10.5 Outcome Data

10.5.1 Engagement in Treatment Survey (Primary Outcome)

At 30, 60, and 90 days post enrollment, participants will be asked to report PrEP use and engagement in PrEP care. The services reported by the patient will be confirmed with the treatment provider or by review of the patient's medical record.

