2.0 STUDY SYNOPSIS

This study will recruit and randomize 80 HIV Pre-Exposure Prophylaxis (PrEP) eligible Emergency Department (ED) patients to facilitated linkage to care for PrEP initiation versus immediate PrEP initiation in the ED (iPrEP) using a PrEP starter pack with facilitated linkage to care. The primary outcome is PrEP usage at 90 days post enrollment. Multiple secondary outcomes will also be measured including retention in care, STI diagnosis, risk behavior and PrEP adherence at 30, 60, and 90 days.

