9.5 Follow-up

All follow-up assessments will be performed over the phone. Follow-up assessments will occur at 30, 60, and 90 days post enrollment.

Follow-up assessments will include:

- 1) Attitudes toward Pre-Exposure Prophylaxis Scale (APS) (Appendix 3)
- 2) Section 4 of ICAP "Screening for Substantial Risk of HIV" (Appendix 5)
- 3) Satisfaction questionnaire and qualitative assessment and visit specific satisfaction instrument (VSQ-9) (Appendix 6)
- 4) Adherence information measured by (1) self-report. Self-report will be assessed with the single measure Guidelines Regimen Information Program (GRIP) guide and questions on last dose and number of missed doses since prior follow-up. (Appendix 7)
- 5) CDC Sexual Behavior Questions (CSBQ) (Appendix 4)
- 6) STAR*D PRISE (Side-effect assessment)

Assessment of engagement in PrEP care at 30, 60, and 90 days post enrollment will be verified by direct contact with the treatment provider/program provided or by EMR review if the patient is linked within the Mount Sinai Health System. If the patient is receiving their PrEP care outside of the Mount Sinai Health System, a signed release authorization form will be sent.

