11.0 DATA MANAGEMENT AND STATISTICAL ANALYSES

11.1 Statistical Analysis

11.1.1 General approach

Nominal and ordinal categorical variables will be summarized as frequencies and percentages. Continuous variables will be summarized with the following descriptive statistics: N, mean, standard deviation, median, minimum, maximum, interquartile range, and range.

No imputation of missing data will be performed for any of the analysis given the pilot nature of the study and small sample size.

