11.1.2 Analysis of Primary and Secondary Outcomes

Analysis will be on an intention-to-treat basis. In statistical analyses, participants will be included to the date of their last active follow-up visit. Comparisons between control and experimental (iPrEP) arms. To assess the success of randomization, a summary of the baseline variables by treatment group will be tabulated and univariate comparisons performed. The primary outcome, retention in care and PrEP usage, will be compared with proportions and Fisher's exact derived confidence intervals. Secondary outcomes: Secondary analysis will focus on determining how retention in care, risk behavior, adherence or STI diagnosis differ between the groups at any of the follow-up time points. PrEP adherence based on pill counts will be calculated by dividing the number of pills taken by the number of pills prescribed. Adherence will be calculated by study month for each participant. Group adherence comparisons will be compared using Wilcoxon rank sum test. Retention in care, STI diagnosis and risk behavior at each time point will be analyzed for each study visit. Retention in care and STI diagnosis will be treated as dichotomous variables for analysis. Measures of risk behavior will include consistency of condom use and number of sexual partners since prior study visit. Condom use will be treated as an ordinal variable and number of sexual partners as a continuous variable for analysis.

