
Reportable Events:

HIV acquired while the patient is taking PrEP is considered a serious adverse event and reported to the IRB within 24 hours. Any pregnancy occurring while on PrEP will be considered a serious adverse event and reported to the IRB within 24 hours.

Data Management, Analysis, and Quality Assurance:

Sources of information will come from the socio-demographic questionnaires, behavioral risk factor questionnaires, PrEP attitude and knowledge measures, satisfaction questionnaires, laboratory test results, adherence questionnaires, electronic medical records and VSQ-9 study visit questionnaires. As noted above all study data will be entered in the electronic data capture (EDC) system that requires unique user Login/Password.

The greatest threat to study validity is likely to be loss to follow-up. We have attempted to minimize this possibility by requiring detailed locator information and performing facilitated linkage. The follow-up rate in our HCV screening program is 50% where there is no requirement for locator data or facilitated linkage. We expect the rates of follow-up in this program to be closer to 85% as was seen in Project BRIEF where facilitated linkage mechanisms were used. We will also collect short term (30-day) and longer term follow-up (60 & 90-days) data to ensure that, even if there is drop-out at each time point, we will still have usable data for outcome analysis.

Given that the study will examine patients presenting to one urban academic emergency department, the results may not generalize to other EDs. We do not see this as problematic as more widespread dissemination first requires some data on the impact of a PrEP screening, initiation and linkage program in the ED setting. We anticipate that the results from this study will set the foundations for a future multicenter R01 that will specifically address generalizability.

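### The plan does not say whether records are checked for a participant missed by phone at day 90; read naturally, section 10.5.1 leaves that participant without a primary value

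*Combined protocol and SAP*

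**What the plan says.** The synopsis (2.0) states: "The primary outcome is PrEP usage at 90 days post enrollment". Section 11.1.2 words it more broadly: "The primary outcome, retention in care and PrEP usage, will be compared with proportions and Fisher's exact derived confidence intervals".

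Section 10.5.1 determines the outcome in two steps. First, at 30, 60 and 90 days, "participants will be asked to report PrEP use and engagement in PrEP care". Then, "The services reported by the patient will be confirmed with the treatment provider" or by record review.

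Section 9.5 makes all follow-up assessments telephone calls. It adds that engagement in PrEP care at the same three time points "will be verified by direct contact with the treatment provider/program provided or by EMR review if the patient is linked" within the health system. It does not make this depend on a completed call.

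For missing values, 11.1.1 states: "No imputation of missing data will be performed for any of the analysis". Section 11.1.2 calls the analysis intention-to-treat but uses participants' data only up to their last active follow-up visit. Section 16.0 keeps people who miss calls in the study, within the 90 days. Section 17.2 lets the investigator remove those who complete no follow-up assessment.

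Access to records is arranged at the start: consent to chart review (12.1.2, 12.3.1) and a release form requested during the ED visit (9.3).

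**The concern.** In 10.5.1 the thing to be confirmed is a service that the participant has reported. If the day-90 call is not completed, nothing has been reported, and the section describes no check. Section 9.5 would allow one. No section says which wording governs a participant who is not reached, or whether that person counts as missing, as a non-user, or as whatever the record shows.

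The rules in section 11 push towards missing. The observed day-90 proportions, and the difference between arms, would then depend on who answers the phone. People who miss calls may well differ in PrEP use from those who answer. Section 17.2 itself names loss to follow-up as the main risk to validity, and the pilot exists to supply planning estimates for a larger trial. Some of this missingness could be avoided with access that the plan already seeks.

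**Working it through.** **1. The wording side by side**

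| Question | 10.5.1 | 9.5 |
|---|---|---|
| What is checked? | Services the participant reported | Engagement in PrEP care |
| Does it need a completed call? | Yes, on its natural reading | Not stated |
| What if the participant is not reached? | Not stated | Not stated |

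Under 10.5.1, no call means no report and no confirmation. Sections 11.1.1 and 11.1.2 then supply no substitute value.

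**2. The plan's own figures**

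The table in 11.1.3 uses 40 per arm, a two-sided pooled Z test and alpha 0.05. I enumerated all pairs of binomial counts and rejected when |Z| was at least 1.96. This reproduces all seven powers to four decimals, for example 0.4581 for 50% vs 70% and 0.8166 for 50% vs 80%. The table therefore assumes that all 80 participants have an outcome value.

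**3. Inputs for the illustration**

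- True day-90 use of 50% (20/40) and 70% (28/40): one row of the table in 11.1.3.
- 15% unreached in each arm (6 of 40, leaving 34): an assumption. Section 17.2 says "We expect the rates of follow-up in this program to be closer to 85" per cent, but that is not a call-completion rate.
- PrEP use among the unreached, q: an assumption, varied below.

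**4. Effect on the observed rates**

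Observed rate = (p − 0.15q) / 0.85.

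| q | Control, true 50% | iPrEP, true 70% | Difference |
|---|---|---|---|
| 0 in both arms | 20/34 = 58.8% | 28/34 = 82.4% | 23.5 points |
| 25% in both arms | 0.4625/0.85 = 54.4% | 0.6625/0.85 = 77.9% | 23.5 points |
| Same as those reached in that arm | 50% | 70% | 20 points |

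Whenever q is the same in both arms, it cancels and the difference is 0.20/0.85 = 23.5 points. If only 70% were reached and all the unreached were non-users, the rates would be 20/28 = 71.4% and 28/28 = 100%, a difference of 28.6 points. That is the arithmetical limit for these true rates.

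**5. Effect on precision and power**

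The Wald 95% half-width is 1.96 × sqrt[(p1(1 − p1) + p2(1 − p2))/n]. It serves only as an approximation, since 11.1.2 specifies Fisher-derived intervals.

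- 40 per arm, 50% vs 70%: 1.96 × sqrt(0.46/40) = 21.0 points.
- 34 per arm, no bias: 1.96 × sqrt(0.46/34) = 22.8 points.
- 34 per arm, observed 58.8% vs 82.4%: 1.96 × sqrt[(0.588 × 0.412 + 0.824 × 0.176)/34] = 20.9 points. Here the interval is no wider, so its width would not reveal the shift.

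Exact pooled-Z power when the unreached are missing at the same use rate:

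| Per arm | 50% vs 70% | 50% vs 80% |
|---|---|---|
| 40 | 0.46 | 0.82 |
| 34 | 0.40 | 0.77 |
| 28 | 0.33 | 0.67 |
| 20 | 0.25 | 0.53 |

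**The case against.** The strongest reply is that the sections do not conflict. Section 10.5.1 describes a check on self-report and does not restrict the check to reported services or forbid a record search when the call fails. Section 9.5 provides for verification at each time point, 10.5.2 has the facility survey completed without condition, and 12.2 lists it as a data source. Read together, these could cover everyone. This stands in part: a reader might infer a flat contradiction, or a stated rule that unreached participants are unscored, and the text supports neither. Section 9.5 does not settle the matter, however, because verifying may equally mean checking what the participant said.

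Two further objections stand.

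- A reader might take 12 of 80 missed calls as the plan's expectation. The 85% in 17.2 comes from a linkage program, 11.1.3 says the team does not expect retention to match that program, and no call-completion rate is given.
- A reader might infer that the record alone can supply the outcome. Section 9.5 verifies engagement in care, and use follows from retention only under an assumption made for the power table. An active prescription does not prove pill-taking. An empty Mount Sinai record does not prove non-use, since care may be elsewhere. For outside clinics, the Appendix 8 survey asks about treatment for alcohol use disorder, so as written it cannot return PrEP data.

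The study is also openly an underpowered pilot that means to measure attrition. That limits the consequences but does not supply the missing rule.

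**Conclusion.** The point holds as a gap in how the primary outcome is ascertained. The natural reading of 10.5.1 with section 11 leaves a participant missed at day 90 without a value, and no section says otherwise, although the means to seek one are arranged at enrollment. The plan should be changed on this point.

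The size is illustrative. With 15% unreached in each arm and none of them using PrEP, a true 20-point difference appears as 23.5 points and both arm rates are overstated, by 8.8 and 12.4 points. If the unreached resemble those reached in their own arm, the only loss is precision, with 34 instead of 40 per arm. Loss falling mainly in one arm could move the difference much further in either direction. A reader might infer such swings, but nothing in the documents supports any particular split, so none is claimed here. How much missingness the record check would remove cannot be stated from the documents.

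**What to change.** 1. In 10.5.1, state that at day 90 the EMR and, where a release is signed, the named PrEP provider will be checked for every randomized participant, whether or not the call is completed. Bring 9.5 into line.
2. Define in advance what record evidence counts as PrEP use covering day 90. Settle at the same time whether the primary outcome is use alone (2.0) or includes retention (11.1.2).
3. Treat an empty Mount Sinai record with no outside-provider information as missing, not as non-use.
4. Report, by arm, how many participants were scored from each source and how many from neither.
5. Add two sensitivity analyses to 11.1.2: one restricted to participants with self-report, and one counting those with neither source as non-users. The second needs a stated exception to the no-imputation rule in 11.1.1.
6. Replace the alcohol use disorder items in Appendix 8 with PrEP items, so that outside clinics can supply the value.

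The cost is some rewording, one revised form and a small number of extra record or clinic checks (0.15 × 80 = 12 if 15% are unreached). The drawback is that record-only cases show prescription or engagement rather than pill-taking, which is why items 4 and 5 are needed.

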10.5.2 Treatment Facility Survey (Appendix 8)

The treatment facility survey will be completed to confirm where the patient is receiving PrEP follow up care. If they are outside of Mount Sinai Health System, they will be sent a signed authorized release form (Appendix 9).

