11.1.3 Sample Size

pilot RCT will be insufficiently powered to provide definitive efficacy data on retention and adherence for two study arms at 90 days. Yet, the pilot data is needed to determine recruitment and attrition rates, as well as means and standard deviations for key measures that will be needed to plan a definitive trial of ED-initiated

PrEP. For illustrative purposes we have included the following table of powers based on different retention in care rates in the control and experimental groups with the assumption that those retained in care will be using PrEP. This analysis assumes initial groups sizes of 40 and 40. The test statistic used is the two-sided Z test with pooled variance. The significance level of the test was targeted at 0.0500.

Power	Control Group	Experimental (iPrEP) Group	Difference in Proportions
	Retained in Care/PrEP	Retained in Care/PrEP	
0.0812	50%	55%	5%
0.1571	50%	60%	10%
0.2859	50%	65%	15%
0.4581	50%	70%	20%
0.6474	50%	75%	20%
0.8166	50%	80%	30%
0.9327	50%	85%	35%

The 50% follow-up rate for the control arm is based on and manuscript by Bogoch et als. entitled “Attrition Between the Emergency Department and Clinic Among Individuals Presenting for HIV Non-occupational Post exposure Prophylaxis published in *Clinical Infectious Diseases* in 2014.⁷⁴ The authors found that only 54% of patients seen in the ED for non-occupational post-exposure prophylaxis attended their first follow-up post-exposure clinic visit. This study did use appointment reminders but not the degree of facilitated linkage that will be used for the described ED PrEP program. In Project BRIEF, the HIV testing program described in the preliminary studies, the follow-up rate for newly infected HIV patients was 85%. Given that this will be the first effort at PrEP screening, initiation and linkage in the Emergency Department we do not expect to achieve the same degree of retention in care as we did for follow-up in Project BRIEF.

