Appendix 8: Treatment Facility Survey

Treatment Facility Survey (ETF)

Date of assessment:

1. What type of provider/program is this?
 - a. Office based provider
 - b. Substance use treatment program
 - c. Inpatient facility
 - d. Other:

2. Was this patient engaged in a program at your facility or being treated at your office for their alcohol use disorder?

If "Yes", please review and answer the following questions.

3. What was the date of their admission into your program, or if office-based, when did their care begin?
4. Indicate the type(s) of treatment they are receiving for their alcohol use disorder:

- a. Naltrexone treatment:

- i. Oral:

- ii. Injectable:

- b. Short-term detoxification

- c. Inpatient

- d. Other:

5. How would you categorize the level of treatment received by this patient?

- a. No care received

- b. Level 1: Outpatient treatment

- c. Level 2: Intensive outpatient treatment (including partial hospitalization)

- d. Level 3: Clinically managed residential/inpatient treatment

- e. Level 4: Medically managed intensive inpatient treatment

- f. Other:

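### Day-90 PrEP usage is the primary outcome, but the planned confirmation covers PrEP care, so use itself rests on self-report

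*Combined protocol and SAP*

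**What the plan says.** Section 2.0 is clear about the outcome: "The primary outcome is PrEP usage at 90 days post enrollment". The instrument labelled as primary is the Engagement in Treatment Survey (Section 10.5.1 under Outcome Data), in which "participants will be asked to report PrEP use and engagement in PrEP care". The next sentence gives the confirmation step: "The services reported by the patient will be confirmed with the treatment provider or by review of the patient's medical record".

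Three other places describe the check:

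- Section 9.5: "Assessment of engagement in PrEP care at 30, 60, and 90 days post enrollment will be verified by direct contact" with the provider, or by review of the electronic record for participants within the health system.
- Section 10.5.2 (Treatment Facility Survey): the form is completed "to confirm where the patient is receiving PrEP follow up care".
- Appendix 8, the form itself: "Was this patient engaged in a program at your facility or being treated at your office for their alcohol use disorder". It goes on to naltrexone, detoxification and level of treatment. It has no item on PrEP prescribing, dispensing or use.

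Section 11.1.2 then names retention and usage jointly as the primary outcome, whereas Sections 7.2 and 21.0 list retention as a secondary outcome. Section 11.1.3 connects the two in its power table "with the assumption that those retained in care will be using PrEP".

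**The concern.** Being in care and taking PrEP are different states, and the protocol expects them to separate. Section 9.3 leaves starting, continuing or stopping PrEP to the participant and the outpatient provider, and Section 17.2 provides for participants who wish to discontinue. Someone can therefore attend the clinic and not be on the drug. If that person reports use on the day-90 call, a check that looks only at care will agree that care took place and will not reveal the error.

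No blinding is described and only one arm leaves the ED with medication, so the tendency to report use could differ by arm. That would move the primary comparison. If care is instead allowed to stand in for use, the primary result becomes the retention result, which is already a separate outcome. Either way the pilot could pass a wrong usage rate to the definitive trial it is meant to inform.

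**Working it through.** **The plan's own figure.** The documents give no figure for misreporting. The nearest is the power table in Section 11.1.3. Exact enumeration of the two-sided pooled Z test (40 per arm, level 0.05, control 50%) returns the stated power in all seven rows to four decimals, for example 0.4581 at 70% and 0.8166 at 80%. The powers are correct, but their input is retention, carried over to use by assumption. The table is no evidence that use is measured.

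**What each source can show about use at day 90**

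| Source | Section | What it establishes |
|---|---|---|
| Participant's answer | 10.5.1, 9.5 | Use, last dose and missed doses, by self-report over the phone |
| Provider contact or record review | 10.5.1, 9.5 | Services or engagement in care; no prescription or refill item is specified |
| Facility survey | 10.5.2, Appendix 8 | Place of care; the items concern alcohol treatment |
| Pill counts | 11.1.2 | Named for secondary adherence only; no routine counting procedure, and Section 9.5 gives self-report by phone |
| Testing by the study team after discharge | 9.3 | None anticipated |

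No row verifies use.

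**Size of a possible false difference.** The documents give no misreporting rates, so these inputs are assumptions:

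- true use π = 0.50 in both arms;
- every true user is in care, and a share u of those in care use PrEP, with u = 0.8 or 0.6;
- the check of care is complete, and a report of use without confirmed care is rejected (the plan does not state this rule);
- a fraction a of non-users over-report: 5% control v 15% iPrEP, or 10% v 30%.

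Retention is π/u, so non-users in care are π/u − π. The false difference is (π/u − π) × (a_iPrEP − a_control).

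- u = 0.8: retention 0.50/0.8 = 62.5%; non-users in care 12.5%. False difference 0.125 × 0.10 = 1.25 points, or 0.125 × 0.20 = 2.5 points.
- u = 0.6: retention 0.50/0.6 = 83.3%; non-users in care 33.3%. False difference 0.333 × 0.10 = 3.3 points, or 0.333 × 0.20 = 6.7 points.
- No check of care: all non-users can be miscounted, so 0.50 × 0.10 = 5 points (52.5% v 57.5%), or 0.50 × 0.20 = 10 points (55% v 65%).

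With 40 per arm, 1.25 points is 0.5 of a participant and 6.7 points is about 2.7. If over-reporting is equal in the two arms, the false difference is zero in this null case.

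**The case against.** The strongest reply is that the check of care does useful work. The starter pack lasts 14 days, so use at day 90 in either arm depends on supply through an outpatient provider. Confirming care tests a necessary condition, and over-reporters who never linked can be caught. This stands, and it is why the 5- and 10-point figures apply only if no check of care is used.

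Several stronger readings are tempting, but the documents do not support them:

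- *Only what the participant reports is checked.* Section 10.5.1 reads that way, but under Section 9.5 engagement "will be verified by direct contact with the treatment provider/program provided or by EMR review", without conditioning on the participant's answer. Participants are also asked to sign a release before discharge and consent to chart review. The two sections need reconciling; neither alone settles the matter.
- *A clinic visit alone counts as success.* No section gives that scoring rule. A record review could show a prescription, though no section says it will be abstracted.
- *The callers are the people who gave out the drug.* No section says so. The case for differential reporting rests only on the absence of described blinding and on the difference between the arms.
- *The power-table assumption defines the outcome.* It is offered as illustration, and the survey asks about use separately.

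It is also fair that this is a pilot with deliberately light data collection (Section 10.1), and that last dose and missed doses are already asked on the same call. That argues for a cheap remedy. It does not remove the need to say what counts as use and which source decides it.

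**Conclusion.** The point holds in a limited form. Followed as written, the plan confirms care and leaves day-90 use as self-report. It never defines usage, it runs retention and usage together in the analysis section, and its facility form cannot collect PrEP information. A participant retained in care who has stopped PrEP but reports use would not be detected by a check of care alone.

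Under the assumed rates the false difference is about 1.3 to 3.3 points for the milder over-reporting and 2.5 to 6.7 points for the heavier. These figures require reporting to differ by arm and unconfirmed reports to be rejected. They show what could happen and do not predict bias. The change should be made because it is inexpensive and because the usage rate is meant to inform a larger trial.

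**What to change.** 1. In Sections 10.5.1 (Engagement in Treatment Survey) and 11.1.2, make PrEP usage at day 90 the sole primary outcome. Score it from the last-dose question already asked on the day-90 call, with a window fixed in advance; the documents give no length. Keep attendance for the retention outcome.
2. Replace the alcohol items in Appendix 8 with PrEP items. At the provider or record contact already planned, record whether a PrEP prescription or refill covers day 90. Do this for every randomized participant with record access, whatever they answered.
3. Reconcile Sections 9.5 and 10.5.1 so that both describe this same check, applied alike in both arms.
4. Pre-specify prescription-supported use, by arm, as a sensitivity analysis.

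The cost is revised wording, a corrected form and one extra data field. Prescription data will be missing where an outside provider does not reply or none is named, and the confirmed rate may fall below the self-reported one. Scoring by last dose is still self-report, and a prescription is only indirect evidence of use. The change therefore narrows the gap without closing it.
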